1. INTRODUCTION

This statistical analysis plan (SAP) describes the statistical analysis methods and data presentations to be used in tables, figures, and listings (TFLs) in the clinical study report (CSR) for Study GS-US-337-1116. This SAP is based on the study Protocol Amendment 6 dated 08 June 2017 and the electronic case report form (eCRF). The SAP will be finalized before database finalization. Any changes made after the finalization of the SAP will be documented in the CSR.

1.1. Study Objectives

The primary objectives of this study are as follows:

- The primary objective of the pharmacokinetics (PK) Lead-in Phase of this study is to evaluate the steady state PK and confirm the dose of Ledipasvir/Sofosbuvir Fixed Dose Combination (LDV/SOF FDC) in hepatitis C virus (HCV)-infected pediatric subjects.
- The primary objective of the Treatment Phase of this study is to evaluate the safety and tolerability of LDV/SOF FDC ± ribavirin (RBV) for 12 or 24 weeks in HCV-infected pediatric subjects.

The secondary objectives of this study are as follows:

- The secondary objective of the PK Lead-in Phase of this study is to evaluate the safety and tolerability of 10 days of dosing of LDV/SOF FDC in HCV-infected pediatric subjects.
- The secondary objectives of the Treatment Phase of this study are:
 - To determine the antiviral efficacy of 12 or 24 weeks of LDV/SOF FDC ± RBV treatment in chronic HCV-infected subjects (including the impact of HCV genotype, IL28B genotype, and prior treatment experience), as assessed by the proportion of subjects with sustained viral response 12 weeks after discontinuation of therapy (SVR12)
 - To determine the antiviral efficacy of 12 or 24 weeks of LDV/SOF FDC ± RBV treatment in chronic HCV-infected subjects, as assessed by the proportion of subjects with sustained viral response 4 and 24 weeks after discontinuation of therapy (SVR4 and SVR24)
 - To evaluate the kinetics of circulating HCV RNA during treatment and after completion of treatment
 - To evaluate the emergence of viral resistance to LDV and SOF during treatment and after completion of treatment
 - To evaluate the acceptability assessed by swallowability of tablets and palatability of granules
 - To evaluate the effect of growth and development on pediatric subjects during and after treatment

The exploratory objective of this study is as follows:

- PPD [Redacted]

1.2. Study Design

This is an open-label, multi-cohort, two-part study evaluating the PK, safety, and efficacy of LDV/SOF FDC ± RBV in chronic HCV-infected pediatric subjects.

The study will enroll both treatment-naïve and treatment-experienced pediatric subjects with up to 40 subjects allowed to be treatment experienced. Approximately 220 total subjects will be enrolled as follows:

- Approximately 100 adolescents aged 12 to < 18 years
- Approximately 120 children aged 3 to < 12 years

Subjects of 3 age groups will be enrolled in a sequential fashion: 12 to <18 years old, followed by 6 to <12 years old, and 3 to <6 years old.

Eligible subjects will receive the following treatment regimens based on HCV genotype, prior treatment experience, cirrhosis status and country of enrollment:

Table 1-1. Subject Enrollment by HCV Genotype, Country, and Treatment Duration

	GT1, GT4, GT5, & GT6		GT1	GT4, GT5, & GT6	GT3
	Cirrhotic or Non-cirrhotic Subjects (TN)	Non - cirrhotic Subjects (TE)	Cirrhotic Subjects (TE)	Cirrhotic Subjects (TE)	Non-cirrhotic or Cirrhotic Subjects (TE)
United States, Australia, New Zealand	12 Weeks of treatment with LDV/SOF FDC	12 Weeks of treatment with LDV/SOF FDC	24 Weeks of treatment with LDV/SOF FDC	12 Weeks of treatment with LDV/SOF FDC	N/A
United Kingdom				24 Weeks of treatment with LDV/SOF FDC	24 Weeks of treatment with LDV/SOF FDC + RBV

TN = Treatment Naïve, TE = Treatment Experienced, N/A = Not Applicable

Therefore, subjects actually enrolled are grouped into the treatment groups according to their age groups, HCV genotype, prior treatment experience, cirrhosis status, and treatment duration, as specified in Section 3.2.

The schedules of assessments for the study are provided as appendixes to the SAP (see Study Procedures Table, [Appendix 1](#)).

1.2.1. PK Lead-in Phase

The PK Lead-in Phase will evaluate and/or confirm the age appropriate LDV/SOF FDC dose by analyzing PK, safety, and antiviral activity of LDV/SOF FDC through 10 days of dosing.

At least 10 treatment-naïve subjects without history of cirrhosis will be sequentially enrolled into each of the following 3 cohorts:

- Cohort 1: 12 to < 18 years old, weighing ≥ 45 kg
- Cohort 2: 6 to < 12 years old, weighing ≥ 17 kg and < 45kg
- Cohort 3: 3 to < 6 years old
 - At least 4 subjects weighing ≥ 17 kg
 - At least 4 subjects weighing < 17 kg

Intensive PK and safety results through Day 10 of each Cohort will be reviewed to confirm the appropriateness of the LDV/SOF FDC dose for that age group as well as to determine the age-appropriate dose to be evaluated in the PK Lead-in Phase of the next age Cohort.

Subjects enrolled in the PK Lead-in Phase will immediately enroll in the Treatment Phase as they complete Day 10 of PK Lead-in. They will continue dosing with LDV/SOF FDC with no interruption of study drug administration until the appropriateness of the dose is confirmed by PK and safety data from the PK Lead-in Phase.

Cohort 1 subjects received LDV/SOF FDC (90 mg/ 400 mg adult tablet or 4×22.5 mg/100 mg tablets if determined necessary based on LDV/SOF FDC swallowability assessment) for 10 days with intensive PK conducted on Day 10.

Cohort 2 subjects received LDV/SOF FDC 45 mg/ 200 mg (2×22.5 mg/ 100 mg tablets) for 10 days with intensive PK conducted on Day 10.

Cohort 3 subjects weighing ≥ 17 kg received LDV/SOF FDC 45 mg/ 200 mg (4×11.25 mg/ 50 mg packets containing granules) for 10 days with intensive PK conducted on Day 10.

Cohort 3 subjects weighing <17 kg received LDV/SOF FDC 33.75 mg/ 150 mg (3×11.25 mg/ 50 mg packets containing granules) for 10 days with intensive PK conducted on Day 10.

1.2.2. Treatment Phase

Additional HCV-infected children will be enrolled into the Treatment Phase upon confirmation of the appropriateness of the dose from the PK Lead-in Phase. The Treatment Phase will be initiated sequentially by age group as defined in Cohorts 1, 2, and 3 of the PK Lead-in Phase.

Subjects who participated in the PK Lead-in Phase will immediately roll over into the Treatment Phase with no interruption of study drug administration until the appropriateness of the dose has been confirmed by PK and safety results from the PK Lead-in Phase. The first visit in the Treatment Phase for these subjects will be the Week 2 visit.

After dose confirmation in the PK Lead-in Phase of each age group, the identical dose was used in subjects of the corresponding age group enrolled in the Treatment Phase.

1.2.3. Study Duration

The total time to complete all study visits is up to approximately 40 weeks for subjects treated with 12 weeks of therapy and 52 weeks for subjects treated for 24 weeks of therapy including the following periods:

- 28-day (4-week) screening period
- 12 or 24 week treatment period
- 24-week posttreatment period

1.3. Sample Size and Power

With approximately 100 subjects enrolled into the 12 to <18 years of age group, a two-sided 95.0% confidence interval of the SVR12 rate will extend at most 5.9% in both directions from the observed SVR12 rate, assuming the expected SVR12 rate is 90%.

With approximately 120 subjects enrolled into the 3 to < 12 years of age group, a two-sided 95.0% confidence interval of the SVR12 rate will extend at most 5.4% in both directions from the observed SVR12 rate, assuming the expected SVR12 rate is 90%.

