9.10. Sample Size

With approximately 100 subjects enrolled into 12 to <18 years (Group 1) of the Treatment Phase, a two-sided 95.0% confidence interval of the SVR12 rate will extend at most 5.9% in both directions from the observed SVR12 rate, assuming the expected SVR12 rate is 90%.

With approximately 120 subjects enrolled into the 3 to < 12 years (Group 2) of the Treatment Phase, a two-sided 95.0% confidence interval of the SVR12 rate will extend at most 5.4% in both directions from the observed SVR12 rate, assuming the expected SVR12 rate is 90%.

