6.1.2. Analysis Methods for the Key Efficacy Endpoint

No inferential statistics will be provided for efficacy endpoints. No statistical comparison will be conducted.

The point estimates of SVR12 rate and 2-sided 95% exact CI based on Clopper-Pearson method will be provided for the SVR12 rate by treatment group and total in each age group {Clopper 1934}.

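### The stated SVR12 precision (at most 5.9 and 5.4 points either way) is a normal-approximation half-width; the exact interval the SAP will report reaches 7.6 and 6.8 points below an observed 90%

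*SAP*

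**What the plan says.** SAP section 1.3 gives the size of each age group and a precision statement for it. The first begins "With approximately 100 subjects enrolled into the 12 to <18 years of age group" and says that the two-sided 95% interval "will extend at most 5.9% in both directions from the observed SVR12 rate, assuming the expected SVR12 rate is 90" per cent. The second begins "With approximately 120 subjects enrolled into the 3 to < 12 years of age group" and says that the interval "will extend at most 5.4% in both directions from the observed SVR12 rate", on the same assumed rate. Protocol section 9.10 carries the same claim ("will extend at most 5.9% in both directions from the observed SVR12 rate"), and so does the Statistical Methods part of the synopsis. None of these places names the interval method.

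The method is named in SAP section 6.1.2: a "2-sided 95% exact CI based on Clopper-Pearson method will be provided for the SVR12 rate", for each treatment group and for the total in each age group. Those age-group totals are the populations that section 1.3 describes. Protocol section 9.6.1 asks only for a point estimate with a 95% confidence interval.

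**The concern.** The precision claim describes an interval that reaches equally far on both sides and never beyond a fixed distance. Neither property holds for a Clopper-Pearson interval around a proportion near 90%. That interval is pulled toward 50%, so its lower arm is the longer one, and both arms change with the observed rate.

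The understated side is the lower limit, which tells a reader how low an SVR12 rate the data are compatible with. The statement is also the only reason either document gives for enrolling about 100 and about 120 subjects in the Treatment Phase. Protocol section 9.4 does reason about precision for the pharmacokinetic comparison, but it concerns a different endpoint and names no sample size.

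**Working it through.** **Inputs.** n = 100 and n = 120, two-sided 95% confidence, and an expected SVR12 rate of 90%, all from SAP section 1.3. At 90% the responder counts are x = 90 and x = 108. The interval method, Clopper-Pearson, comes from SAP section 6.1.2.

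**Step 1: reproduce the stated figures.** The Wald half-width is 1.96 × √(p(1 − p)/n).

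- n = 100: 1.96 × √(0.09/100) = 5.88 points, which rounds to 5.9.
- n = 120: 1.96 × √(0.09/120) = 5.37 points, which rounds to 5.4.

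None of the alternatives tried gives both stated figures:

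| Method | n = 100 | n = 120 |
|---|---|---|
| Wald with continuity correction | 6.38 | 5.78 |
| Clopper-Pearson, average half-width | 6.36 | 5.77 |
| Wilson (below / above) | 7.44 / 4.48 | 6.67 / 4.19 |
| Agresti-Coull (below / above) | 7.61 / 4.65 | 6.80 / 4.32 |
| Jeffreys (below / above) | 7.01 / 4.74 | 6.31 / 4.42 |

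**Step 2: compute the planned interval.** The lower limit is the 0.025 quantile of Beta(x, n − x + 1). The upper limit is the 0.975 quantile of Beta(x + 1, n − x).

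| | 95% exact CI | Below | Above | Stated maximum | Lower arm / stated |
|---|---|---|---|---|---|
| 90/100 | 82.38% to 95.10% | 7.62 | 5.10 | 5.9 | 7.62/5.9 = 1.29 |
| 108/120 | 83.18% to 94.73% | 6.82 | 4.73 | 5.4 | 6.82/5.4 = 1.26 |

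The lower arm exceeds the stated maximum by 7.62 − 5.9 = 1.7 points and 6.82 − 5.4 = 1.4 points. The upper arm stays inside it.

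**Step 3: ask how often the stated maximum would be exceeded.** At the rates that matter here, the exact lower arm stays within 5.9 points only with at least 97/100 responders (5.52 points at 97, 5.93 at 96). It stays within 5.4 points only with at least 115/120 (5.29 at 115, 5.57 at 114). Summing binomial probabilities over the remaining counts:

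| True SVR12 rate | n = 100 | n = 120 |
|---|---|---|
| 90% | 0.99 | 0.98 |
| 95% | 0.74 | 0.56 |

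**Step 4: apply the same test to the Wald interval.** Its half-width also grows as the observed rate falls below 90%: it is 6.13 points at 89/100 and 5.56 at 107/120. With a true rate of 90%, it exceeds the stated figure with probability 0.42 for each group.

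**Step 5: put the gap on the sample-size scale.** In steps of 10 subjects, an observed 90% would need 160 subjects before the exact lower arm fits within 5.9 points (5.73 points at 160), and 180 before it fits within 5.4 (5.34 at 180). This only shows the size of the discrepancy and is not a case for enlarging the trial.

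**The case against.** The strongest reply is that nothing depends on these figures. SAP section 6.1.2 rules out inferential statistics and comparisons for efficacy. Neither document sets an SVR12 target, historical control or power, and the primary Treatment Phase endpoint is adverse events leading to permanent discontinuation of study drug. The reported interval is fully specified, so readers will see the correct asymmetric limits whatever section 1.3 says. The SAP's treatment groups already reflect the subjects enrolled, so the sentence can no longer influence recruitment. All of this stands. It limits the consequence but does not make the stated precision true.

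A second reply is that 5.9 and 5.4 are correct as normal-approximation planning values. That also stands: the arithmetic is right for a Wald interval, and the fault lies in attaching an unlabelled, symmetric maximum to an analysis that uses another method.

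A third is that the sentence is conditional ("assuming the expected SVR12 rate is 90" per cent). Read as meaning 90% or better, the Wald half-width does stay within the stated figures. This weakens the Step 4 point, which depends on observed rates below 90%. It does not help the exact interval, which breaks the bound at 90% itself and, on the lower side, at every observed rate from there up to 96/100 or 114/120.

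Finally, the protocol names no interval method, so it does not contradict itself. The conflict is between SAP sections 1.3 and 6.1.2. The protocol and synopsis nevertheless state a precision that the planned analysis will not deliver.

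**Conclusion.** The concern holds. The stated maxima of 5.9 and 5.4 points are Wald half-widths at 90%. The prespecified exact interval extends 7.6 and 6.8 points below an observed 90%, and 5.1 and 4.7 points above it. At the documents' own assumed rate the lower arm is almost certain to exceed the stated maximum (99% and 98%).

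These sizes assume exactly 100 and 120 subjects in the age-group totals. The distances in points also assume an observed rate of exactly 90%; they change with the observed rate, and the smaller treatment groups within each age band will have wider intervals. The practical effect is modest, since no conclusion or sample size changes. The text should still be corrected, because it is the stated basis for the Treatment Phase group sizes and is wrong on its less favourable side.

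**What to change.** In SAP section 1.3, Protocol section 9.10 and the synopsis, replace the two precision sentences with wording such as: *If the observed SVR12 rate is 90%, the two-sided 95% exact (Clopper-Pearson) confidence interval is 82.4% to 95.1% with 100 subjects and 83.2% to 94.7% with 120 subjects.* Remove the words that promise a maximum and the same reach on both sides.

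A weaker alternative is to keep 5.9% and 5.4%, label them as normal-approximation half-widths at an observed 90%, and drop the claim that they are maxima.

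The cost is a text edit. The sample size and the analysis stay as they are, and the stated precision becomes slightly less favourable.

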2. TYPE OF PLANNED ANALYSIS

2.1. DMC Analyses

An external multidisciplinary data monitoring committee (DMC) will review the progress of the study and perform interim reviews of safety data and provide recommendation to Gilead about whether the nature, frequency, and severity of adverse effects associated with study treatment warrant the early termination of the study in the best interests of the participants, whether the study should continue as planned, or the study should continue with modifications.

Specific activities of the DMC will be defined by a mutually agreed charter, which will define DMC membership, conduct and meeting schedule.

2.2. Final Analysis

After all subjects have completed through the post-treatment week 24 visit or have prematurely discontinued from the study, outstanding data queries have been resolved, and the database has been cleaned and finalized, the final analysis of the data will be performed.

3. GENERAL CONSIDERATIONS FOR DATA ANALYSES

Analysis results will be presented using descriptive statistics. For categorical variables, the number and percentage of subjects in each category will be presented; for continuous variables, the number of subjects [n], mean, standard deviation [SD] or standard error [SE], median, first quartile [Q1], third quartile [Q3], minimum, and maximum will be presented.

Data collected in the study will be presented in by-subject listings for all subjects in the Safety Analysis Set, unless otherwise specified. All by-subject listings will be presented by subject identification (ID) number in ascending order, unless otherwise specified.

3.1. Analysis Sets

Analysis sets define the subjects to be included in an analysis. Analysis sets and their definitions are provided in this section. The number of subjects eligible for each analysis set will be provided. Subjects who were excluded from Safety and Full Analysis Sets will be provided in a by-subject listing with reasons for exclusion.

3.1.1. All Enrolled Analysis Set

All Enrolled Analysis Set includes all subjects enrolled in the study after screening. All analyses based on the All Enrolled Analysis Set will be performed according to the treatment group to which subjects were enrolled.

3.1.2. Full Analysis Set

The Full Analysis Set (FAS) includes HCV infected subjects who were enrolled into the study and received at least one dose of study drug. The study drugs in this study include LDV/SOF FDC and RBV. Subjects are grouped within the FAS by the treatment group to which they were enrolled.

This is the primary analysis set for efficacy analyses.

3.1.3. Safety Analysis Set

The Safety Analysis Set includes all subjects who took at least 1 dose of study drug (ie, LDV/SOF FDC ± RBV). Subjects will be grouped according to the treatment they actually received.

This is the primary analysis set for safety analyses.

3.1.4. Pharmacokinetic Analysis Set

PK Lead-in Phase Intensive PK Analysis Set

The PK Lead-in Phase Intensive PK Analysis Set includes all PK Lead-in Phase subjects who received at least one dose of study drug and for whom at least one non-missing PK concentration

data value is available from the PK Lead-in Phase intensive sampling. This is the primary analysis set for PK Lead-in Phase intensive PK analysis.

Population PK Analysis Set

The Population PK Analysis Set includes all enrolled subjects who received at least one dose of study drug and for whom at least one non-missing PK concentration data value is available from the PK sampling. This is the primary analysis set for the Population PK modeling and PK exposure analyses.

The PK Analysis Set is equivalent to the Population PK Analysis Set.

3.2. Subject Grouping

For analyses based on the All Enrolled Analysis Set or FAS, subjects will be grouped according to the treatment to which they were enrolled. For analyses based on the Safety Analysis Set, subjects will be grouped according to the actual treatment received. The actual treatment received is defined as the enrolled treatment except for subjects who received treatment that differs from the enrolled treatment for the entire treatment duration. In this case, the actual treatment received is defined as the treatment received for the entire treatment duration.

Generally, subjects are analyzed, except for the safety analysis, by treatment groups based on age group, HCV genotype, prior treatment experience, cirrhosis status, and treatment duration:

Table 3-1. Non-safety Treatment Groups*

12 to < 18 Years Old		3 to < 12 Years Old			
LDV/SOF (90/400 mg) 12 Weeks		LDV/SOF (45/200 mg or 33.75/150 mg) 12 Weeks		LDV/SOF (45/200 mg) 24 Weeks	LDV/SOF+RBV (45/200 mg) 24 Weeks
GT1 TN w/ or w/o cirrhosis (N =)	GT1 TE without cirrhosis (N =)	GT1, GT4 TN w/ or w/o cirrhosis (N =)	GT1 TE without cirrhosis (N =)	GT1 TE with cirrhosis (N =)	GT3 TE w/ or w/o cirrhosis (N =)
6 to < 12 Years Old			3 to < 6 Years Old		
LDV/SOF (45/200 mg) 12 Weeks		LDV/SOF (45/200 mg) 24 Weeks	LDV/SOF+RBV (45/200 mg) 24Weeks	LDV/SOF (45/200 mg or 33.75/150 mg) 12 Weeks	
GT1, GT4 TN w/ or w/o cirrhosis (N =)	GT1 TE without cirrhosis (N =)	GT1 TE with cirrhosis (N =)	GT3 TE w/ or w/o cirrhosis (N =)	GT1, GT4 TN w/ or w/o cirrhosis (N =)	

GT = genotype, TN = Treatment Naïve, TE = Treatment Experienced, w/ = with, w/o = without
 *Treatment Groups reflect the subjects actually enrolled.

For the safety analysis, subjects will be analyzed by the following groups based on age group, treatment regimen and duration:

Table 3-2. Safety Treatment Groups

12 to < 18 Years Old	3 to < 12 Years Old		
LDV/SOF (90/400 mg) 12 Weeks (N =)	LDV/SOF (45/200 mg or 33.75/150 mg) 12 Weeks (N =)	LDV/SOF (45/200 mg) 24 Weeks (N =)	LDV/SOF+RBV (45/200 mg) 24 Weeks (N =)
6 to < 12 Years Old			3 to < 6 Years Old
LDV/SOF (45/200 mg) 12 Weeks (N =)	LDV/SOF (45/200 mg) 24 Weeks (N =)	LDV/SOF+RBV (45/200 mg) 24 Weeks (N =)	LDV/SOF (45/200 mg or 33.75/150 mg) 12 Weeks (N =)

Subjects in the 3 to < 6 years of age group will have additional selected efficacy and safety analyses performed according to baseline weight in the following subgroups:

Table 3-3. Subgroups for Selected Analyses in 3 to < 6 years of Age

3 to < 6 Years Old	
< 17 kg LDV/SOF (33.75/150 mg) 12 Weeks (N =)	≥ 17 kg LDV/SOF (45/200 mg) 12 Weeks (N =)

3.3. Strata and Covariates

This study does not use a stratified randomization schedule for enrolling subjects. No covariates will be included in efficacy and safety analyses.

3.4. Examination of Subject Subsets

The efficacy endpoint SVR12 will be analyzed for the following subsets:

- sex (male, female)
- race (black, non-black)
- ethnicity (Hispanic or Latino, non-Hispanic or Latino)
- baseline weight (≤ median, > median)

- IL28B (CC, non-CC [further broken down to CT, TT])
- baseline HCV RNA ($< 800,000$ IU/mL, $\geq 800,000$ IU/mL)
- baseline ALT ($\leq 1.5 \times$ ULN, $> 1.5 \times$ ULN)
- Interferon (IFN) eligibility (IFN-eligible, IFN-ineligible)
- most recent response to prior HCV treatment (non-response, relapse/breakthrough, IFN-intolerant) for treatment experienced subjects
- study treatment status (completed study treatment, discontinued study treatment)
- adherence to study regimen ($< 80\%$, $\geq 80\%$).

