For the Treatment Phase, the primary safety endpoint is any AE leading to permanent discontinuation of study. The key efficacy endpoint is SVR12 in all enrolled and treated subjects. Point estimate of SVR12 rate and its 95% confidence interval will be provided for each age group.

Acceptability of the study treatments will be summarized using descriptive statistics by assessing swallowability of tablets and palatability of granules as applicable. Clinically relevant subgroup analysis on SVR12 may be conducted as appropriate (i.e., assuming that adequate numbers of patients in the subsets are available for analysis).

All continuous endpoints will be summarized using an 8-number summary (n, mean, standard deviation, median, Q1, Q3, minimum, and maximum). All categorical endpoints will be summarized by number and percentage of subjects who meet the endpoint definition.

Safety endpoints will be analyzed by the number and percent of subjects with events or abnormalities for categorical values or 8-number summary (n, mean, standard deviation, median, Q1, Q3, minimum, maximum) for continuous data.

With approximately 100 subjects enrolled into 12 to <18 years (Group 1) of the Treatment Phase, a two-sided 95.0% confidence interval of the SVR12 rate will extend at most 5.9% in both directions from the observed SVR12 rate, assuming the expected SVR12 rate is 90%.

With approximately 120 subjects enrolled into the 3 to < 12 years (Group 2) of the Treatment Phase, a two-sided 95.0% confidence interval of the SVR12 rate will extend at most 5.4% in both directions from the observed SVR12 rate, assuming the expected SVR12 rate is 90%.

This study will be conducted in accordance with the guidelines of Good Clinical Practices (GCPs) including archiving of essential documents.

GLOSSARY OF ABBREVIATIONS AND DEFINITION OF TERMS

° C	degrees Celsius
° F	degrees Fahrenheit
AE	adverse event
ALT	alanine aminotransferase (also SGPT)
ANC	absolute neutrophil count
APTT	activated partial thromboplastin time
AST	aspartate aminotransferase (also SGOT)
AUC	area under the curve
AUC _{tau}	area under the plasma concentration versus time curve over the dosing interval (tau)
BLQ	below the lower limit of quantification
BMI	body mass index
CK	creatine kinase
C _{max}	the maximum observed serum/plasma/peripheral blood mononuclear (PBMC) concentration of drug
C _{tau}	observed drug concentration at the end of the dosing interval (tau)
CRF	case report form(s)

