2. OBJECTIVES

The primary objective of the PK Lead-in Phase of this study is:

- To evaluate the steady state pharmacokinetics (PK) and confirm the dose of LDV/SOF FDC in chronic HCV-infected pediatric subjects

The secondary objective of the PK Lead-in Phase of this study is:

- To evaluate the safety, tolerability, and antiviral activity of 10 days of dosing of LDV/SOF FDC in chronic HCV-infected pediatric subjects

The primary objective of the Treatment Phase of this study is:

- To evaluate the safety and tolerability of LDV/SOF FDC +/- RBV for 12 or 24 weeks in chronic HCV-infected pediatric subjects

The secondary objectives of the Treatment Phase of this study are:

- To determine the antiviral efficacy of 12 or 24 weeks of LDV/SOF FDC +/- RBV treatment in chronic HCV-infected subjects (including the impact of HCV genotype, IL28B genotype, and prior treatment experience), as assessed by the proportion of subjects with SVR 12 weeks after completion of treatment (SVR12)
- To determine the antiviral efficacy of 12 or 24 weeks of LDV/SOF FDC +/- RBV treatment in chronic HCV-infected subjects, as assessed by the proportion of subjects with SVR 4 and 24 weeks after completion of treatment (SVR4 and SVR24)
- To evaluate the kinetics of circulating HCV RNA during treatment and after completion of treatment
- To evaluate the emergence of viral resistance to LDV and SOF during treatment and after completion of treatment
- To evaluate acceptability
- assessed by swallowability of tablets and palatability of granules.
- To evaluate the effect of growth and development on pediatric subjects during and after treatment

The exploratory objective of this study is:

- PPD

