9.6.3. Subgroup Analysis

Subgroup analysis on SVR12 will be performed by treatment experience and cirrhosis status, by IL28B genotype, and by HCV genotype. Other clinically relevant subgroup analyses may be conducted as appropriate (i.e., assuming that adequate numbers of subjects in these subsets are available for analysis).

Details on efficacy analyses will be described in the statistical analysis plan.

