5.2. Other Baseline Characteristics

Other baseline characteristics include:

- weight in kg
- height in cm
- body mass index (BMI; in kg/m²)
- HCV genotype (genotype 1 [further broken down to 1a, 1b, and other], genotype 3, genotype 4, and other as applicable)
- cirrhosis (presence, absence, unknown)
- IL28B (CC, CT, TT)
- baseline HCV RNA (log₁₀ IU/mL) as a continuous variable and as categories (< 800,000 IU/mL, ≥ 800,000 IU/mL)
- baseline ALT (U/L) as a continuous variable and as categories (≤1.5 × ULN, > 1.5 × ULN)
- estimated glomerular filtration rate (eGFR) using Schwartz Formula (mL/min/1.73m²)
- prior treatment experience (treatment naïve, treatment experienced)
- IFN eligibility (IFN-eligible, IFN-ineligible)

- most recent response to prior HCV treatment (non-response, relapse/breakthrough, IFN-intolerant) for treatment experienced subjects
- mode of HCV Infection
- bone age in years
- Tanner Stage

Estimated Glomerular Filtration Rate (GFR) will be calculated using Schwartz Formula ($\text{mL}/\text{min}/1.73\text{m}^2 = k \times L/\text{Scr}$ [(k is a proportionality constant, for adolescent females ≥ 12 years old is 0.55; for adolescent males ≥ 12 years old is 0.70, and for children 3- <12 years old is 0.55); L is height in centimeters (cm); and Scr is serum creatinine (mg/dL)]

These baseline characteristics will be summarized by treatment group and total in each age group using descriptive statistics (n, mean, SD, median, Q1, Q3, minimum, and maximum) for continuous variables and using the numbers and percentages of subjects for categorical variables. The summary of baseline characteristics will be provided for the Safety Analysis Set.

In addition, for subjects 3 to < 6 years of age, baseline characteristics will be summarized by treatment group as defined in [Table 3-3](#) and total.

A by-subject listing of other baseline characteristics will be provided by subject ID number in ascending order.

[figure not shown]

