6.1.3. Subgroup Analysis of the Key Efficacy Endpoint

The point estimates of SVR12 rate and 2-sided 95% exact CIs based on Clopper-Pearson method will be provided for each treatment group within each subgroup specified in Section 3.4 {Clopper 1934}.

A Forest plot will graphically present estimates and 95% confidence intervals of SVR12 rates for each treatment group within each subgroup.

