6.4. Changes From Protocol-Specified Efficacy Analyses

There are no changes from protocol-specified efficacy analyses.

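### The SAP omits the SVR12 subgroup analyses by HCV genotype and cirrhosis status that the protocol commits to, Table 3-1 replaces them only in part, and SAP 6.4 records no change

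*SAP*

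**What the plan says.** Protocol 9.6.3: "Subgroup analysis on SVR12 will be performed by treatment experience and cirrhosis status, by IL28B genotype, and by HCV genotype". A separate sentence there allows other clinically relevant subgroups if numbers are adequate. The Statistical Methods part of the synopsis is softer and names no factor: "Clinically relevant subgroup analysis on SVR12 may be conducted as appropriate". The secondary efficacy objective in protocol section 2, repeated in SAP 1.1, is to determine SVR12 "including the impact of HCV genotype, IL28B genotype, and prior treatment experience".

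SAP 3.4 begins "The efficacy endpoint SVR12 will be analyzed for the following subsets" and lists sex, race, ethnicity, baseline weight, IL28B, baseline HCV RNA, baseline ALT, interferon eligibility, response to prior treatment, study treatment status and adherence. SAP 6.1.3 says the estimates and exact intervals "will be provided for each treatment group within each subgroup specified in Section 3.4".

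The main SVR12 display (SAP 6.1.2) is by treatment group and by age-group total. The treatment groups are the columns of Table 3-1, one of which is "GT1, GT4 TN w/ or w/o cirrhosis". SAP 5.2 summarises HCV genotype and cirrhosis (present, absent or unknown) at baseline. SAP 6.4 states: "There are no changes from protocol-specified efficacy analyses".

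On the Lead-in, protocol 9.6.2 specifies a summary of HCV RNA values and change from baseline at each visit, and protocol 6.3.2 has HCV RNA drawn on Day 3. SAP 3.7.2 takes the Week 1 record of Lead-in subjects from Day 10. SAP 1.1 states the Lead-in secondary objective as safety and tolerability only, whereas protocol section 2 includes antiviral activity.

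**The concern.** Of the four factors named in protocol 9.6.3, the SAP subset list keeps only IL28B. Treatment experience survives through Table 3-1, because every column is wholly naive or wholly experienced. HCV genotype and cirrhosis survive only in part.

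Genotype is the more important loss because it is part of a stated objective. As planned, the report would give no SVR12 rate or interval for GT4 children; a reader could only trace individual failures through listings. Cirrhosis is not in the objective, but it is named in protocol 9.6.3. Anyone relying on SAP 6.4 would not know that analyses named in the protocol had been left out.

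**Working it through.** **1. The protocol's factors against the SAP**

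| Protocol factor | In SAP 3.4? | Separated by Table 3-1? |
|---|---|---|
| IL28B (9.6.3) | Yes | not needed |
| Treatment experience (9.6.3) | No | Yes, in every column |
| HCV genotype (9.6.3) | No | In part: adolescents are GT1 only, GT3 has its own column, GT1 experienced has its own columns; GT1 and GT4 are pooled in treatment-naive under-12s |
| Cirrhosis (9.6.3) | No | Only for GT1 experienced subjects under 12; adolescents have only a non-cirrhotic GT1 experienced column |
| Lead-in HCV RNA at each visit (9.6.2) | No table found | not applicable |

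**2. Columns of Table 3-1**

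- Printed columns: 2 (12 to <18) + 4 (3 to <12) + 4 (6 to <12) + 1 (3 to <6) = 11.
- GT1 and GT4 pooled: 3 of 11. Cirrhotic and non-cirrhotic pooled: 6 of 11 (treatment-naive in all four age blocks, GT3 in two).
- The 3 to <12 block is the union of the two younger blocks. Without it there are 2 + 4 + 1 = 7 columns, of which 2 pool genotype and 4 pool cirrhosis.

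No visible estimate therefore isolates GT4, GT1-only treatment-naive children under 12, treatment-naive cirrhotics, or GT3 by cirrhosis. The Table 3-1 footnote says the groups reflect actual enrolment, so the labels imply that GT4 children were enrolled in both younger age groups.

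**3. The plan's own precision figure**

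Wald half-width = 1.96 × √(0.9 × 0.1 / N). For N = 100 this is 5.88 points and for N = 120 it is 5.37 points, matching the stated 5.9 and 5.4.

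**4. What a pooled rate can show**

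Shift in the pooled rate = GT4 share × GT4 deficit. The documents give no GT4 count, so the share is an assumption.

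| Assumed GT4 share | Shift for a 20-point GT4 deficit |
|---|---|
| 2% | 0.02 × 20 = 0.4 points |
| 5% | 0.05 × 20 = 1.0 point |
| 10% | 0.10 × 20 = 2.0 points |

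At a 10% share, a shift of 5.4 points would need a deficit of 5.4 / 0.10 = 54 points. The 5.4 is for all of Group 2, about 120 subjects; a single treatment-naive column is smaller, so its own interval would be wider.

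**5. Is a GT4 deficit expected?**

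Not on the documents' adult data (protocol 1.2.1, 12 weeks of LDV/SOF), with exact 95% intervals:

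- 41/44 = 93.2% (81.3 to 98.6)
- 20/21 = 95.2% (76.2 to 99.9)
- together 61/65 = 93.8% (85.0 to 98.3)

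The point is only that the planned displays could not show a deficit or its absence.

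**6. Lead-in Day 3**

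The Week 1 window is Days 2 to 11 with nominal Day 7. The explicit rule takes Day 10 for Lead-in subjects, so Day 3 enters no by-visit summary in the visible text. For a visit on Day 10 exactly, the general closest-record rule agrees: |10 − 7| = 3 against |3 − 7| = 4. The protocol allows a late visit (to Day 13, or Day 14 after non-compliance), where the general rule alone could differ, but the explicit rule governs.

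**The case against.** The strongest reply is that these factors were not dropped but moved: SAP 3.2 builds its treatment groups on genotype, treatment experience and cirrhosis, and SAP 6.1.2 gives an exact interval for each group. That is right for treatment experience, for GT3, for adolescents' genotype, and for cirrhosis in GT1 experienced children. It is not right for the pooled columns in step 2.

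The synopsis makes subgroup work conditional on adequate numbers, and the pooling may follow known small counts. But protocol 9.6.3 applies that condition only to other subgroups, and the SAP gives no such reason. It also plans exact intervals for subsets likely to be sparse, such as subjects who discontinued treatment or were less than 80% adherent.

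Several points do stand. All efficacy analyses are descriptive and secondary. By-subject listings already let a reader trace individuals. A very small GT4 stratum would be uninformative: even 10/10 has a lower limit of 69.2%, so a true rate of 75% could not be excluded. The adult benchmark of 61/65 includes treatment-experienced and cirrhotic subjects, whereas the pooled paediatric columns are treatment-naive; the adult naive figure in the first study is 21 responders, given as 96%. SAP 6.3 and part of protocol 9.6.2 are redacted, so the finding covers the visible text only. These points limit the consequence but do not make SAP 6.4 correct.

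**Conclusion.** The concern holds and should be corrected. SAP 3.4 and 6.1.3 leave out two SVR12 subgroup factors specified in protocol 9.6.3, Table 3-1 restores them only in part, and the statement in SAP 6.4 is wrong on the visible text. The missing Lead-in HCV RNA summary is a second unrecorded departure.

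The loss is one of reporting, not of a test or decision: the genotype part of the secondary objective goes unanswered for GT4. Over the assumed GT4 shares of 2% to 10%, a 20-point deficit would appear as at most 2.0 points in the pooled rate. No deficit is presumed, and the actual GT4 and cirrhotic counts are not in the documents.

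**What to change.** - Add HCV genotype, and cirrhosis status by treatment experience, to SAP 3.4 and the forest plot, with Clopper-Pearson intervals within age group. Keep unknown cirrhosis as its own level, as in SAP 5.2.
- Where a stratum is very small, give one by-subject listing of genotype, cirrhosis and SVR12 outcome instead.
- Add a descriptive Lead-in table of HCV RNA (value and change from baseline) by cohort at Day 1, Day 3 and Day 10.
- Correct SAP 6.4 to record any protocol-specified analysis not done, with the reason.

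The cost is a few table rows or one listing, plus one Lead-in table, all from data already collected. The drawback is wide intervals in small strata: with all subjects responding, 2/2 gives 15.8 to 100%, 5/5 gives 47.8 to 100%, and 10/10 gives 69.2 to 100%.
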